#### **4.3 TREATMENT COMPLIANCE**

Patients are requested to bring all remaining trial medication including empty package material with them when attending visits.

Based on tablet counts, treatment compliance will be calculated as shown in the formula below. Compliance will be verified by the CRA authorised by the Sponsor or delegate.

$$\text{Treatment compliance (\%)} = \frac{\text{Number of tablets actually taken}}{\text{Number of tablets which should have been taken as directed by the Investigator}} \times 100$$

If the number of doses taken is not between 80-120%, site staff will explain to the patient the importance of treatment compliance.

## 5. ASSESSMENTS

### 5.1 ASSESSMENT OF EFFICACY

#### 5.1.1 Hepatic venous pressure gradient

HVPG measurement will be performed at the time points specified in the [Flow Chart](#). Sites must have access to the necessary infrastructure and equipment to measure HVPG (e.g. a hepatic haemodynamic laboratory at their site, or at a nearby institution). Site staff performing the procedure must have sufficient expertise (e.g. performing in the region of 25 or more HVPG measurements per year) with interventional skills and expertise in the reading of pressure tracings, since a local interpretation of the tracing from Visit 1c will be required for eligibility purposes (refer to [Section 3.3.2](#)).

The HVPG procedure within the trial will be conducted in a standardised fashion at all sites (for details refer to the HVPG manual in the ISF); training will be provided. Each trial site will be asked to provide acceptable sample HVPG tracing(s) prior to commencing patient recruitment if not already provided for Trial 1366-0021. Measurements of wedged hepatic venous pressure (WHVP) and free hepatic venous pressure (FHVP) will be performed in triplicate; tracings will be provided to an external Supplier and read centrally by independent expert(s) in PH; the central read will include a subjective assessment of the overall trace quality as well as a read of the relevant pressures. The independent expert(s) will be blinded to the timepoint that the trace relates to. The central read will include the traces from Visit 1c that have also been interpreted locally. The results of the central read will be transferred to the Sponsor and will be considered the official evaluation of the trial. In case of discrepancies between a local interpretation and the central evaluation (e.g. of the Visit 1c tracing), the central evaluation will remain valid.

HVPG measurements should be performed using the same hepatic vein, prior to intake of the trial medication, after an overnight fast, and ideally in the morning. If it is not possible to perform the measurement at Visit 1c in the morning an alternative time of day can be chosen; in this case, a fast of at least four hours is required. The subsequent HVPG measurement must then be performed at approximately the same time of day as the Visit 1c measurement for a single patient.

[figure not shown]
If Visit 1b and 1c are performed on the same day, the HVPG measurement must be performed after the gastroscopy (i.e. only once it is confirmed that the patient remains eligible for the trial). At the EoT visit, the HVPG measurement should be performed on the day of the scheduled visit, or within seven days (if this latter approach is taken, the measurement should still be performed after an overnight fast / after a fast of at least four hours). If this scenario is chosen for an HVPG performed during the treatment period, the morning dose of trial medication can be taken prior to the procedure. In the event of early discontinuation from the trial, refer to [Section 6.2.2.1](#) for guidance regarding the HVPG measurement at the ED visit.

*A summary of the HVPG procedure is as follows ([R20-3977](#)):*

Under local anaesthesia and ultrasound guidance, a catheter introducer sheath is placed in the right internal jugular vein. Using fluoroscopic guidance, a balloon catheter is advanced into

Proprietary confidential information © 2023 Boehringer Ingelheim International GmbH or one or more of its affiliated companies

the inferior vena cava (IVC) and inserted into a large hepatic vein. Correct and sufficient wedge position of the catheter is ensured by injecting contrast media while the balloon is blocking the outflow of the cannulated hepatic vein. After calibrating the external pressure transducer, continuous pressure recordings are obtained with triplicate recordings of the WHVP and FHVP. The difference between FHVP and WHVP is referred to as HVPG, with values  $\geq 10$  mmHg indicating CSPH. Before removing the catheter, pressure readings obtained in the IVC at the same level, as well as the right atrial pressure, are recorded.

## **5.2 ASSESSMENT OF SAFETY**

### **5.2.1 Physical examination**

A complete physical examination must be performed at the two time points specified in the [Flow Chart](#); further physical examinations are only required if the patient reports symptoms. A complete physical examination includes, as a minimum, general appearance, neck, lungs, cardiovascular system, abdomen, extremities and skin.

#### **5.2.1.1 Anthropometric measurements (height, weight, waist and hip circumference)**

Measurement of height, body weight, waist and hip circumference will be performed at the time points specified in the [Flow Chart](#). Height will be measured at Visit 1a only. The results of anthropometric measurements must be included in the source documents available at the site.

Whenever possible, weight measurements should always be performed on the same weighing scales for one patient. In order to get comparable body weight values, the assessment should be performed in the following way:

- shoes, coat / jackets and any headgear should be taken off
- pockets should be emptied of heavy objects (i.e. keys, coins etc)
- after bladder voiding

The measuring tape used for waist and hip circumference should be made of a material that is not easily stretched, such as fiberglass. Waist circumference measurements should be made around a patient's bare midriff, after the patient exhales while standing without shoes and with both feet touching and arms hanging freely. Waist circumference should be determined by measuring the midpoint between the lowest rib and the iliac crest. The tape should be placed perpendicular to the long axis of the body and horizontal to the floor and applied with sufficient tension to conform to the measurement surface.

Hip circumference measurements should start at one hip, wrapping the measuring tape around the widest part of the buttocks, and around the other hip to the front. Coats / jackets should be taken off and pockets emptied to ensure a close measurement and with both feet touching and arms hanging freely.

---

 Headgear worn for religious reasons is acceptable, but this should be worn for all weight measurements in the trial

## 5.2.2 Vital signs / home blood pressure and heart rate monitoring

Vital signs (SBP, DBP, as well as HR [pulse rate]) will be evaluated at trial visits at the time points specified in the [Flow Chart](#), prior to blood sampling and prior to the 12-lead ECG. BP measurements should be recorded in the eCRF to the nearest 1 mmHg. BP measurements should be performed on the non-dominant arm. HR should be measured electronically or by palpation, and counted for one minute. BP and HR measurements should be taken after patients have rested quietly, in the seated / supine position, for at least 5 minutes. The measurements recorded at the trial visit must be included in the source documents available at the site.

At screening (Visit 1a), the site should use their preferred method to measure vital signs. From Visit 2 onwards, vital signs should be measured using the patients home BP monitoring equipment (refer to [Section 5.2.2.1](#)) in order to have a consistent method for the duration of the trial. This includes the pre- and post-dose vital signs measurements during the dose-titration period and at the subsequent visit (refer to the Flow Chart and [Section 6.2](#)).

### 5.2.2.1 Home blood pressure and heart rate monitoring

Home BP and HR monitoring will be performed by the patient as specified in the [Flow Chart](#). Electronic BP and HR monitoring equipment will be provided for this purpose. Site staff will train the patient in the correct use of the equipment at Visit 2, explaining that it must be used only to record BP and HR measurements belonging to the patient. Subsequent refresher training should be provided at subsequent visits if required.

Patients will be asked to measure their BP and HR every day in the morning, soon after waking up prior to much physical activity, and after resting seated for approximately 5 minutes. Measurements must be taken before administration of the morning dose of trial medication. The electronic readings will be stored in the memory of the home BP and HR monitoring equipment.

If, at any time after trial medication intake, a patient experiences symptoms suggestive of hypotension (e.g. he / she feels light-headed / dizzy, sees black spots, suffers from weakness etc.), particularly if the symptoms occur whilst standing up, or if he / she has any other symptoms in between trial visits, additional BP and HR reading(s) can be taken and the patient should report these symptoms at the next trial visit. The patient should bring the home BP and HR monitoring equipment with them to each trial visit (refer to the [Flow Chart](#)) for the site staff to review the electronic readings, and to use for the measurement of BP and HR during trial visits from Visit 2 onwards (refer to [Section 5.2.2](#)). Any BP / HR measurements which, following review, are evaluated as AEs, must be included in the source documents available at the site (refer to [Section 8.3.1](#)).

## 5.2.3 Safety laboratory parameters

Safety laboratory parameters that will be assessed are listed in [Table 5.2.3: 1](#). Sampling time points will be as indicated in the Flow Chart. All analyses will be performed by a central laboratory; the respective reference ranges will be provided in the ISF. Refer to [Table 5.2.3:2](#)

for a list of “minimum required safety laboratory parameters” in the event of force majeure or other disruptive circumstances.

Patients should be fasted for blood sampling for the safety laboratory where that visit is defined as a fasting visit in the [Flow Chart](#); where a non-fasting status is defined, the safety laboratory sample can be collected in a non-fasting status. The fasting status will be recorded for e.g. [REDACTED] Blood samples for safety laboratory parameters should be drawn prior to administration of trial medication.

Instructions regarding sample collection, sample handling / processing and sample shipping will be provided in the central laboratory manual in the ISF.

The central laboratory will provide laboratory reports to the Investigator. It is the responsibility of the Investigator to evaluate these reports. Clinically relevant abnormal findings, as judged by the Investigator, must be reported as AEs (refer to [Section 5.2.6](#)).

Laboratory tests may need to be repeated in case of required medical follow-up due to an AE or if a test was not successful due to incorrect specimen handling or storage. Should a patient not fulfil all laboratory requirements to take part in the trial due to a transitional medical condition, the patient may continue in the screening period but cannot be randomised until the re-test of the laboratory result is available to determine the eligibility of the patient (refer to [Section 3.3](#)).

In case that the criteria for hepatic injury are fulfilled, a number of additional measures will be performed (refer to [Section 5.2.6.1.4](#) for the DILI checklist which can be downloaded from the electronic data capture [eDC] system, and [Appendix 10.2](#)). The amount of blood taken from the patient concerned will be increased due to this additional sampling.

The CKD-EPI formula (isotope dilution mass spectrometry standardised) will be used for reporting eGFR based on serum creatinine.

The central laboratory will transfer the results of the analysis to the Sponsor or delegate.

In case that the qualitative parameters are abnormal, a quantitative analysis will be performed by the central laboratory.

Table 5.2.3: 1

Safety laboratory tests

Category	Test name	Short Name (BI Laboratory Test Code, LBSPID)
Haematology	Haematocrit Haemoglobin MCV MCH MCHC RBC count / erythrocytes RBC distribution width (RDW) WBC count / leukocytes Platelet count / thrombocytes Reticulocytes	HCT HGB MCV MCH MCHC RBC RDW WBC PLTCT RETABS
Automatic WBC differential (absolute and percentage)	Neutrophils Eosinophils Basophils Monocytes Lymphocytes	SEGABS EOSABS BASABS MONABS LYMABS
Coagulation	aPTT PT INR Fibrinogen	APTTS PRTSEC INR FIBR
Clinical chemistry	ALT Alpha fetoprotein  Albumin Alkaline phosphatase AST Bilirubin (total) Bilirubin (direct) Bilirubin (indirect) Brain Natriuretic Peptide (BNP) HbA1c  hs-CRP Creatinine, serum CK CK-MB  eGFR γ-GT Glucose, plasma LDH Lipase Protein (total)	SGPT AFP ALB ALKP SGOT TBILI BILID BILII BNP HBA1C CRPHS CRE CK CKMBABS GFRE GGT GLUB LDH LIPASE TPRO

Table 5.2.3: 1 Safety laboratory tests (cont)

Category	Test name	Short Name (BI Laboratory Test Code, LBSPID)
Clinical chemistry	Troponin I  Urea (BUN) Uric acid	TPONI UREA URIC
Electrolytes	Bicarbonate Calcium Chloride Magnesium Phosphate Potassium Sodium	BICARB CA CL MG P K NA
Lipids 	HDL LDL Cholesterol (total) Triglycerides	HDL LDL CHOL TRIGL
Hormones	Insulin, plasma  Aldosterone  Renin, plasma  TSH  Free T3  Free T4 	INS ALDOSI PRCSP TSH FT3 FT4V
Pregnancy test (serum)	Human Chorionic Gonadotropin 	HCG
Pregnancy test (urine)	Human Chorionic Gonadotropin 	Not Applicable
Infections screening 	HCV antibody (qualitative) HCV RNA PCR  HBV surface antigen (qualitative) HBV core antibody (qualitative) HBV – DNA 	HCAB HCVRNA HBSAG HBCAB HBVDNAV
Urine chemistry	Urine albumin	UALBUM
Urinalysis (semi-quantitative)	Urine nitrite Urine protein Urine glucose Urine ketone Urobilinogen Urine bilirubin Urine blood Urine leukocyte esterase Urine pH	UNIT UPROZ UGLU UKET UROBZ UBILI UHGB ULEUKES UPH

1 Only performed at screening (Visit 1a) and EoT / ED

2 If initial CK is elevated, re-test CK with CK-MB and troponin I

3 Not performed at screening (Visit 1a)

Proprietary confidential information © 2023 Boehringer Ingelheim International GmbH or one or more of its affiliated companies

- 4 Not performed at screening (Visit 1a) or EoS; collect seated after patient seated for at least 5 to 15 minutes, and once patient has been out of bed for at least 2 hours
- 5 Only performed at screening (Visit 1a)
- 6 Reflex in case of abnormal TSH
- 7 WOCBP only; only at Visit 1a, and as a reflex if urine testing is positive
- 8 WOCBP only, Visit 2 onwards. Measured locally at the site every 4 weeks using a pregnancy test kit provided by the central laboratory. Serum pregnancy testing will be done as a reflex if urine testing is positive (see above). More frequent pregnancy testing should be done if required by local regulation and /or authority or per investigator judgement. Pregnancy testing at dosing visits should be completed prior to administration of the trial medication
- 9 Reflex in case of positive HCV antibody. Per central laboratory assay, if HCV RNA is < 15 IU/ml at screening, eligibility criteria are met.
- 10 Reflex in case of positive HBV core antibody. Per central laboratory assay, if HBV DNA is < 20 IU/ml at screening, eligibility criteria are met.
- 11 For calculation of HOMA-IR at visit 2, 5, EoT and EoS

Based on the analysis of Fasting Plasma Insulin (FPI) and Fasting Plasma Glucose (FPG), the HOMA index to assess insulin resistance will be derived in the following way:

$$\text{HOMA-IR} = \frac{(FPI \times FPG)}{22.5}$$

Note: FPI (mU/L), FPG (mmol/L)

A factor of 0.05549 will be used to convert FPG values from mg/dL to mmol/L for calculation of HOMA-IR

Table 5.2.3: 2      Minimum required safety laboratory tests (force majeure / other disruptive circumstances)

Category	Test name	Short Name (BI Laboratory Test Code, LBSPID)
Haematology	Haemoglobin RBC count / erythrocytes WBC count / leukocytes Platelet count / thrombocytes	HGB RBC WBC PLTCT
Clinical chemistry	ALT Albumin Alkaline phosphatase AST Bilirubin (total) Creatinine Potassium Sodium	SGPT ALB ALKP SGOT TBILI CRE K NA

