		
will be excluded from the trial (refer to Sections 3.3.3 and 4.2.2.1).
 
ECGs will be performed at each visit in the randomised treatment period of the trial, and trial medication will be discontinued in the event of a prolonged QT / QTcF-interval (refer to Section 3.3.4.1).

Risks related to drug-drug interaction (DDI)	Refer to Section 1.2.1	
Close monitoring of patients for AEs and restricted co-administration of impacted concomitant therapies such as treatments with a similar mechanism of action (i.e. activators of the NO-sGC-cGMP pathway), clinically relevant therapies inhibiting the activity of OATP1B1/3 and clinically relevant UGT inhibitors. Patients taking concomitant therapies that are sensitive CYP3A4 and CYP2C8 substrates and / or narrow therapeutic index CYP3A4 and CYP2C8 substrates will also be monitored closely. A list, to support the identification of the above-mentioned concomitant therapies at trial sites, will be provided in the Investigator Site File (ISF). Also refer to Sections 3.3.3 and 4.2.2.1.

**Table 1.4.2:2** Overview risks - Investigational Medicinal Product Empagliflozin

Possible / known risks of clinical relevance	Summary of data, rationale for the risk	Mitigation strategy
Potential adverse effects such as ketoacidosis, genital infections, complicated UTI (pyelonephritis, urosepsis), Fournier's gangrene, hypoglycaemia (with concomitant use of insulin or sulfonylurea), and volume depletion	Primarily related to the mechanism of action	
To minimise the risk of severe or serious side effects, participants of this trial will only be exposed to doses that have been safely administered to healthy volunteers and patients in trials, and that are commercially available.
 
Patients at higher risk of adverse effects related to the study drug will be excluded from the trial according to the exclusion criteria in Section 3.3.3.
 
Study treatment will be stopped in patients with suspected ketoacidosis or

Table 1.4.2:2      Overview risks - Investigational Medicinal Product Empagliflozin  
 (cont)

Possible / known risks of clinical relevance	Summary of data, rationale for the risk	Mitigation strategy

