### **3. DESCRIPTION OF DESIGN AND TRIAL POPULATION**

#### **3.1 OVERALL TRIAL DESIGN**

This phase II multi-national, randomised, open-label and parallel group trial to investigate the effects of oral BI 685509 alone and in combination with empagliflozin on portal hypertension after 8 weeks treatment in patients with clinically significant portal hypertension (CSPH) in compensated cirrhosis.

Patients will be enrolled in the trial and screened for eligibility once they have signed the informed consent. The screening period consists of up to 3 visits (Visits 1a, b and c) and will last a maximum of 6 weeks. Patients will be able to progress from one visit to the next when eligibility of the previous visit is confirmed. Assessments will include a gastroscopy (if applicable – refer to [Section 5.2.5.2](#)), ultrasound of the liver and spleen, [REDACTED] [REDACTED] and measurement of HVPG. Patients who remain eligible and who successfully complete this period will proceed to the 8-week open label, active treatment period.

In total, 80 patients with HBV, HCV or NASH (with or without T2DM) will enter the trial with a minimum of 20 patients in the NASH treatment group 3 and a minimum of 20 patients in the NASH treatment group 4.

NASH patients without diagnosis of T2DM can only enter treatment group 3 ([REDACTED] BID BI 685509 alone) at Visit 2. NASH patients with diagnosis of T2DM will be randomized at visit 2 in a 1:1 ratio into either treatment group 3 ([REDACTED] BID BI 685509 alone) or treatment group 4 ([REDACTED] BID BI 685509 + 10mg QD empagliflozin) Although randomization is applied, the patients, investigators and sponsors will stay unblinded due to the open-label nature of this trial.

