### 3.2 DISCUSSION OF TRIAL DESIGN, INCLUDING THE CHOICE OF CONTROL GROUP(S)

A randomised, open-label and parallel group design has been chosen for this exploratory trial with a very short treatment period, on top of standard of care. The parallel group will enable comparison of four different patient groups and the open label design will provide benefit to all patients participating in it.

A treatment duration of 8 weeks has been chosen to allow an evaluation of short-term efficacy and indirect comparison to the week 8 results from trial 1366-0021.

The patient population of this trial (HBV, HCV and NASH patients with and without T2DM) has been chosen as it represents a sub-set of the intended patient population for BI 685509 (patients with clinically significant portal hypertension in compensated cirrhosis due to non-cholestatic liver diseases). In parallel, Trial 1366-0021 is conducted to investigate efficacy and safety of BI 685509 in alcohol-related liver disease (ARLD) patients with a treatment duration of 24 weeks. The 8-week interim analysis data of Trial 1366-0021 and the final data of this trial will allow evaluation of the short-term efficacy and safety of BI 685509 on portal hypertension in the most common liver diseases. The aim of this study is to evaluate, whether the portal pressure can be reduced in a similar fashion as in trial 1366-0021 in patients with ARLD, and therefore no placebo arm is needed.

In Arm 4, a combination of BI 685509 and empagliflozin will be investigated exploratorily to assess the additional benefit of metabolic improvement by a SGLT2 inhibitor, in this study empagliflozin, in patients with NASH and T2DM.

For details regarding the choice of renal function in the patient population, refer to [Section 1.2](#).

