10. Alpha-fetoprotein  $>$  50 ng/mL ( $>$  50  $\mu$ g/L) at screening (Visit 1a), measured by the central laboratory
11. An active infection with SARS-CoV-2 (or who is known to have a positive test from screening [Visit 1a] until randomisation [Visit 2])
12. Prior orthotopic liver transplantation
13. Prior or planned TIPS or other porto-systemic bypass procedure
14. Known portal vein thrombosis
15. History of clinically relevant orthostatic hypotension, fainting spells or blackouts due to hypotension or of unknown origin (based on Investigator judgement)
16. QTcF-interval  $>$  450 ms in men or  $>$  470 ms in women at screening (Visit 1a), a family history of long QT syndrome, or concomitant use of therapies with a known risk of Torsade de Pointes or planned initiation of such therapies during the trial (refer to [Section 4.2.2.1](#))
17. Type 1 diabetes mellitus, or history of other autoimmune causes of diabetes mellitus (e.g. LADA)
18. Patients at increased risk of ketoacidosis in the opinion of the investigator.
19. Contraindication to any of the trial assessments (e.g. poor patient co-operation for gastroscopy, [REDACTED] etc.)
20. Major surgery (major according to the investigator's assessment) performed within 12 weeks prior to randomisation (Visit 2) or planned during the trial, e.g. hip replacement.
21. Any documented active or suspected malignancy or history of malignancy within 5 years prior to screening (Visit 1a), except appropriately treated basal cell carcinoma of the skin or in situ carcinoma of uterine cervix

Proprietary confidential information © 2023 Boehringer Ingelheim International GmbH or one or more of its affiliated companies

22. History of (in the 6 months prior to randomisation [Visit 2]), or ongoing, chronic drug abuse, or not expected to comply with the protocol requirements for any other reason that, based on Investigator judgement, makes the patient an unreliable trial recruit or unlikely to complete the trial as scheduled
23. Previous randomisation in this trial, previous exposure to BI 685509, or an allergy / contraindication to BI 685509 and / or empagliflozin and / or any of the excipients
24. Currently enrolled in another investigational device or drug trial, or less than 30 days or 5 half-lives (whichever is longer) prior to randomisation (Visit 2) since ending another investigational device or drug trial, or receiving other investigational treatment(s)

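### HOMA-IR is derived from measured insulin with no rule for insulin-treated patients, in whom the index does not measure insulin resistance

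*Protocol*

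**What the plan says.** Protocol Section 5.2.3 states that "the HOMA index to assess insulin resistance will be derived in the following way": FPI x FPG / 22.5. It fixes the units ("Note: FPI (mU/L), FPG (mmol/L") and the glucose conversion ("A factor of 0.05549 will be used to convert FPG values from mg/dL to mmol/L for calculation of HOMA-IR"). The footnote to plasma insulin in Table 5.2.3: 1 gives purpose and timing: "For calculation of HOMA-IR at visit 2, 5, EoT and EoS". Neither the formula nor the footnote limits the population, although the pregnancy-test footnotes to the same table do carry a population limit. The table contains no C-peptide.

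On who may enter, the diabetes exclusion in Section 3.3.3 reads "Type 1 diabetes mellitus, or history of other autoimmune causes of diabetes mellitus (e.g. LADA". A separate criterion lets the investigator exclude patients thought to be at raised risk of ketoacidosis. Neither names insulin treatment of T2DM. Insulin is not among the restricted therapies of Section 4.2.2.1, and Section 4.2.1 allows chronic background treatment at a stable dose. The empagliflozin risk table in Section 1.4.2 lists "hypoglycaemia (with concomitant use of insulin or sulfonylurea", so the protocol foresees concomitant insulin.

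On allocation, Section 3.1 says "NASH patients with diagnosis of T2DM will be randomized at visit 2 in a 1:1 ratio into either treatment group 3" or group 4, while NASH patients without T2DM can enter only group 3.

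The visible SAP does not mention HOMA-IR. An insulin dose change is not a listed intercurrent event (SAP Section 6.3), and no subgroup analyses are planned (SAP Section 7.5.2).

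**The concern.** HOMA-IR can be read as insulin resistance only when the measured insulin is the patient's own response to the measured glucose. In a patient who injects insulin, the assay reads endogenous plus injected insulin, or misses some of the injected product. Either way the number is not on the same scale as in a patient without insulin. No dose change is needed for this: the Visit 2 value is already affected.

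The problem is unlikely to be spread evenly. Every group 4 patient has T2DM, while group 3 combines randomised T2DM patients with NASH patients who do not have it. Insulin use is therefore likely to be more frequent in group 4 by construction, and no visible summary of HOMA-IR separates patients by diabetes status or insulin use. What is at stake is the reading of one descriptive metabolic measure, chiefly when group 4 is set beside group 3.

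**Working it through.** **The plan's own figure.** The conversion factor is sound. With a molar mass of glucose of 180.156 g/mol (not in the documents), 10/180.156 = 0.05551 against the stated 0.05549, a 0.03% difference.

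**Inputs.** From the documents: the formula, and about 20 patients per group. Assumed: the share *s* of measured insulin that is injected, the cut *c* in insulin dose, the change *g* in fasting glucose, and the fraction *f* of an arm using insulin. Endogenous insulin is held fixed.

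**Level of the index.** Take FPG 8 mmol/L and endogenous insulin 15 mU/L (both assumed).

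- No injected insulin in the sample: 15 x 8 / 22.5 = 5.33.
- With 30 mU/L injected insulin detected: 45 x 8 / 22.5 = 16.0.
- Arm of 20 with 4 users: (16 x 5.33 + 4 x 16.0)/20 = 7.47, which is 40% above 5.33.
- Arm of 20 with 8 users: (12 x 5.33 + 8 x 16.0)/20 = 9.60, which is 80% above 5.33.

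Endogenous insulin and glucose are the same in all these patients.

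**Change within one insulin user.** Relative change = (1 - *s* x *c*) x (1 + *g*) - 1.

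| Injected share *s* | Dose cut *c* | FPG change *g* | HOMA-IR change |
|---|---|---|---|
| 30% | 10% | 0 | -3% |
| 50% | 20% | 0 | -10% |
| 50% | 20% | -10% | -19% |
| 50% | 20% | +10% | -1% |
| 100% | 50% | 0 | -50% |
| 30% | 10% | +10% | +6.7% |
| 0% (product not detected) | any | +10% | +10% |

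The sign turns when *g* exceeds 1/(1 - *s* x *c*) - 1. That is 11.1% for a 50% share and 20% cut, and 3.1% for a 30% share and 10% cut.

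**Shift in an arm's mean percentage change.** If every user in the arm has the same cut, and glucose and the non-users do not change, the shift is -*f* x *s* x *c*.

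| Users *f* | Share *s* | Cut *c* | Shift (points) |
|---|---|---|---|
| 20% (4 of 20) | 50% | 20% | -2.0 |
| 20% | 70% | 30% | -4.2 |
| 50% (10 of 20) | 50% | 20% | -5.0 |
| 50% | 100% | 20% | -10.0 |
| 50% | 70% | 30% | -10.5 |
| 50% | 100% | 30% | -15.0 |

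The last row is the extreme corner of the assumed ranges.

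**The case against.** Four arguments can be made against the point.

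- **Redaction.** Section 5.2.3 is a laboratory section and does not set an analysis population. The further endpoints in Protocol Section 2.2.2 are blacked out, and so are several entries in the SAP table of contents. A restriction to patients without insulin may stand there. This is a real limit on the point, and the fix is conditional on it.
- **Existing summaries.** SAP Section 7.3 tabulates concomitant medication by class and preferred name, and glucose already receives baseline, last-value and change summaries under SAP Section 7.8.1. Insulin use will therefore be visible as a count, but a count is not linked to the HOMA-IR values. Medians and quartiles are also planned, which limits the pull of a few large values without making those values valid.
- **Low consequence.** No hypothesis is tested and further endpoints are descriptive. This stands.
- **Randomisation.** Within T2DM patients, insulin use at entry is balanced in expectation between groups 3 and 4. That is true, but it does not carry over to group 3 as a whole.

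A reader might go further and infer that the error favours the combination, because insulin would be cut when empagliflozin starts. The documents do not support this. No visible text calls for an insulin reduction, Section 4.2.1 speaks of stable background doses, the assay is not described, and an undetected product or a rise in glucose moves the index the other way.

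A large false improvement is equally unsupported. In the example above, a fall from 16.0 to 5.33, or 67%, needs all injected insulin to be removed with glucose unchanged.

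Nor does Section 3.2 make HOMA-IR the yardstick for Arm 4. It says the arm is there "to assess the additional benefit of metabolic improvement by a SGLT2 inhibitor" and names no insulin-resistance index, in a trial whose primary endpoint is HVPG.

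**Conclusion.** The point holds as a gap in a derivation rule. As written, Section 5.2.3 yields a HOMA-IR value for insulin-treated patients that does not measure insulin resistance, and such patients are neither excluded nor restricted. Because group 4 is all T2DM and group 3 is mixed, the contamination is likely to be unequal between them.

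The direction of any bias in change from baseline cannot be settled from the documents. Its size is conditional on figures the documents do not give: about 2 to 10 points of an arm's mean percentage change in most scenarios worked, 15 at the corner, with unchanged glucose and a dose cut in every user. If insulin doses stay stable, as Section 4.2.1 anticipates, the change from baseline is less affected and the distortion lies mainly in the level. The issue is minor: it concerns one descriptive measure and leaves HVPG and the secondary endpoints untouched.

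**What to change.** In Protocol Section 5.2.3 and the SAP, unless a redacted section already does so:

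1. Summarise HOMA-IR and its change from baseline in patients not using insulin at Visit 2.
2. Show baseline insulin users separately, with a note that the value is not to be read as insulin resistance.
3. Flag visits after a new insulin start, and give the summary with and without those visits.

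The population is defined by insulin use at baseline, because requiring patients to remain off insulin afterwards would select on treatment given after randomisation and could remove patients unequally from groups 3 and 4. No extra glucose summary is needed.

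The change uses concomitant therapy already recorded in the eCRF and adds no sample or visit. Its cost is a smaller N in one descriptive table and a few more rows. If a restriction already exists in a redacted section, a cross-reference from Section 5.2.3 is enough.
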